10. DATA MANAGEMENT

Data Collection. All data will be in the form of interview and self-report questionnaires for psychological outcomes included with this document. Demographic data will be collected, but no uniquely identifying participant data will reside with, or be linked to actual responses to questionnaires. Patients will complete clinical interviews and self-report measures assessing emotional state and symptoms at intake (Baseline/Week0), week 6, week 12 and week 24. Week 0 measures are only re-administered if

time since baseline is over 4 weeks. All assessments will be audiotaped and study personnel will listen to a randomly selected 20% to ensure reliability over the course of the study. We will also collect administrative data to examine utilization of VA care the 6 months prior to randomization and 6 months following treatment.

The study assessments will be administered online through the Charleston VA's academic affiliate, Medical University of South Carolina (MUSC) REDCap™ (Research Electronic Data Capture) software. REDCap™ is a software toolset and workflow methodology for electronic collection and management of research clinical trial data. It provides secure, web-based flexible applications, including real time validation rules with automated data type and range checks at the time of entry. The underlying database is hosted in a secure data center at MUSC, a secure environment for data systems and servers on campus, and includes redundancy, failover capability, backups and extensive security checks. The system has several layers of protection including user/group account management, "Data Access Groups" which allow data to be entered by multiple groups in one database with segmented user rights for entered data, audit trails for all changes, queries and reports, and Secure Sockets Layer (SSL) encryption. The administration of study assessments will be conducted and monitored by the study staff through a password-protected REDCap account. Only research team members will have access to the data. Data will remain on REDCap and will be uploaded to the VA secure network until it is verified as de-identified per HIPAA regulation. All paper forms will be held in a locked filing cabinet in the recruiting Site PI's locked research offices. Study data will be collected by study ID only via REDCap. REDCap data will regularly be backed up and exported to the VA secure server. At the study's conclusion, the electronic crosswalk file linking study IDs with patient identifiers will be destroyed per MUSC and VA policy.

See Table 1 for a summary of the assessments and timing of administration. Assessments will be administered in person whenever possible. However, in order to accommodate participant schedules and/or instances in which a participant may have left the local area at the time of a follow up assessment, we may collect full or partial assessments in person or via phone or electronic data capture using a secure link to the HIPAA-compliant REDCap database. Reasonable efforts will be made to collect all data as described in this protocol, but we expect some participants may not be able to complete part or all of any given follow-up assessment.

Table 1. Research Materials.

Instrument	Wk 0	Wk 6	Wk 12	Wk 24
1. LEC	X			
2. CAPS5	X	X	X	X
3. WHODAS	X	X	X	X
4. C-SSRS	X	X	X	X
5. Health Interview		X	X	X
6. Demo & Military Service Characteristics	X			
7. B-IPF	X	X	X	X
8. PCL-5*	X	X	X	X
9. PHQ-9*	X	X	X	X
10. PTCI	X	X	X	X
11. CES	X			
12. CEQ	X	X	X	X

13. MINI (AUD/SUD modules only)	X			
14. COVID-19 Research Therapy Impact Questionnaire		X	X	X

*These measures will be administered for PE-PC treatment sessions as well as all assessment time points.

1. Primary Outcome **World Health Organization Disability Assessment Schedule (WHODAS)**: The WHODAS is a brief assessment instrument (36-item version) used to assess health and disability across six domains of functioning: cognition, mobility, self-care, getting along, life activities and participation. The WHODAS has excellent psychometric properties, including high overall internal consistency ($\alpha = .96$) and test-retest reliability (0.98).
2. Brief Inventory of Psychosocial Function (B-IPF): The B-IPF is a recently developed brief self-report of function. Since the measure is new, we will examine the measure's utility within this patient population and its sensitivity to show treatment change coincident with the well-established WHODAS.
3. Clinician Administered PTSD Scale-5 (CAPS5): CAPS is an interview measure of PTSD severity and the primary outcome measure for the study. Current PTSD will be assessed by IEs in relation to the trauma that is currently most upsetting. The CAPS5 has excellent psychometrics and requires about 45 minutes to complete. 20% of CAPS will be rated by a second rater to ensure reliability.
4. PTSD Checklist – Stressor-Specific Version (PCL-5): The PCL-5 is a 20-item self-report measure of PTSD severity in the past month with 4 subscales: Intrusion symptoms (items 1- 5); Avoidance symptoms (items 6-7); negative cognitions and mood symptoms (items 8-14) and Hyperarousal symptoms (items 15-20). Each item ranges from 0 (not at all) to 4 (extremely). Cut points and psychometrics are pulled from the most recent studies on the new PCL-5.
5. Patient Health Questionnaire – 9 (PHQ-9): The PHQ-9 is a 9 item, well-validated measure of depression and secondary outcome. The PHQ-9 assesses symptoms of major depression in the past two weeks from 0 (not at all) to 3 (nearly every day) and has excellent internal and test-retest reliability as well as construct and criterion validity. The PHQ-9 was demonstrated effective in detecting treatment changes in depression in PC settings.
6. Demographic & Military Service Characteristics: This form assesses standard demographics (ethnicity, sex, age) and military service information (e.g., rank).
7. Columbia-Suicide Severity Rating Scale (C-SSRS): C-SSRS will be used to assess past suicide ideation. The C-SSRS will be administered by an IE.
8. Posttraumatic Cognitions Inventory (PTCI): The Posttraumatic Cognitions Inventory (PTCI) is a 36-item self-report of negative thoughts about the self, negative thoughts about the world, and self-blame. The scale has good psychometrics and change in these thoughts has been related to change in PTSD symptoms with treatment.
9. Health Interview: The Health Interview includes items regarding general health, hospitalizations, current and past psychiatric medications, utilization of MH services, utilization of outpatient medical services, and caffeine and tobacco use. Items will be minimized to prevent redundancy with information pulled from medical record and other sources. After treatment, we also ask about changes in military status and important life events since the last interview.
10. Combat Experiences Scale: CES is a seven-item measure of combat exposure severity and enquires about the frequency of various combat experiences. Total scores range from 0 to 41. The CES has demonstrated good reliability and will characterize the sample and be considered as a potential moderator.
11. Life Events Checklist (LEC): LEC is a 17-item measure of self-reported potentially traumatic life events endorsed as happened to me, saw it happen to someone else, and heard about it. LEC (e.g.,

number of life- events) will be used to characterize the sample and be considered as a potential moderator.

12. Credibility and Expectancy Questionnaire (CEQ): The CEQ is a 6-item measure that was designed to assess treatment expectancy and rationale credibility of interventions examined clinical outcomes studies. The scale has demonstrated high internal consistency and test-retest reliability.

13. Mini-International Neuropsychiatric Interview (MINI): The MINI is a brief structured interview that assesses the criteria for DSM-V Axis I diagnoses. The MINI exhibits similar sensitivity and specificity to more time-intensive structured psychiatric interviews. The MINI will be used to screen for severe alcohol and/or substance use.

14. Mental health and medical services utilization: Receiving the PE-PC intervention may lead to a change in the health care utilization pattern for VA patients. Therefore, we will collect utilization data for all VA health services received by the study patients 24 weeks prior to study enrollment as well as the 24-week period of study enrollment. This will allow us to analyze both within-patient and between-patient changes in resource utilization patterns due to the intervention. We will use data on patient clinical status, health services use, and pharmacy use obtained from VA Decision Support Systems (DSS) Medical SAS Outpatient and Inpatient data, and the National Patient Care Database (NPCD). We will also use Non-VA Medical Care (formerly Fee Basis) files to incorporate financial and limited clinical information on covered care provided to VA patients outside of VA facilities. Outpatient visits will be defined as a clinical encounter with a VA MH clinician (e.g., psychologist, psychiatrist, social worker), PC provider (for MH brief intervention or psychiatric medications), VA tele-psychiatrist or tele-psychologist, or community (non-VA) MH provider. As a part of PCMHI care, each PE-PC sessions will be included as an outpatient encounter. Each PE-PC sessions will be recorded and considered as an outpatient encounter. We will examine the number of outpatient MH visits and the number of MH inpatient admissions. Medical services utilization will be defined as the number of PC outpatient visits, ED, and inpatient medical admissions during follow-up.

15. COVID-19 Research Therapy Impact Questionnaire: Ten-item questionnaire which assesses impact of the COVID-19 pandemic on research participation and daily life.

16. Other Covariates: We will assess patient comorbidity burden during the 24 weeks prior to enrollment using the Charlson Comorbidity Index (CCI).

Evaluator Training. All evaluators will be blind to treatment condition and will be trained to criterion on CAPS5 prior to study start. Interviews will be recorded for use in recalibration and interrater reliability assessment. All IEs will complete bi-monthly recalibration assessment reviews for CAPS5.

Protection of Patient Confidentiality/Disposition of Data. Protection of participant confidentiality is an important component of subject protection. The main potential risk to subjects is violation of their confidentiality. We will take careful precautions to maintain confidentiality for all subjects, using procedures we have used with similar previous studies: The investigators and the research team will sign a confidentiality agreement with the Charleston VAMC that no identifying information of specific individuals will appear in any internal reports prepared for the VA or external documents (e.g., peer-reviewed publications, presentations). All study data related to psychological outcomes (i.e., the participant responses to questionnaires) and demographics will not have any unique identifying data commingled or attached in any way. There will be no linkage between a volunteer's identity and their responses. The master list of participants (again, not linked to any participant responses) will remain on the VA secure network in an encrypted folder, and the document itself will be encrypted with a password for an added measure of protection. All data will be stored in locked files or on encrypted computers in the PI's research offices.

When study results are published or presented, only aggregate reports of the results will be used and subjects' identity will not be revealed. All analyses will be conducted on de-identified data only. All paper documents will be securely stored in locked filing cabinets. Access to research records (paper and computerized) will be restricted to the project staff. Specifically, access to de-identified study data will be limited to named project investigators, the project coordinator, VAMC audit personnel, and MUSC IRB audit personnel. The list of participant names will be kept separate from all data and will be available only to on-site project staff.

Data will be maintained per VA protocols, and not less than two years prior to permanent storage. We will seek guidance regarding VA policies for maintenance terms of psychological data to determine the exact period of time that will elapse upon completion of which all study records will be stored permanently.

Data regarding sensitive information such as HIV status or illegal residency will not be collected. Rather, only demographic and psychological outcome data will be collected. However, State and Local authorities do require reporting of potentially suicidal or homicidal behavior. These exceptions to confidentiality will be clearly explained to volunteers during the informed consent process.

All investigators and project personnel have completed a certified program of instruction in the protection of human subjects in research, such as the VA website tutorial, NIH website tutorial or the University of Miami CITI course.

Data Protection. Data will be coded using an assigned number. Data collected on paper will be placed into locked cabinets in study offices at the Ralph H. Johnson or surrounding CBOC. Electronically captured data, as well as audio/video recordings, will be uploaded to a secure database. Every member of the research team will be trained and monitored about how to handle and protect both medical and research records. Furthermore, the research team strictly controls access to study data. These audio files will only be used for the purpose of fidelity to ensure the treatment is being delivered in accordance with the treatment manual for this study only. Upon study termination, and once the data has been analyzed to the fullest extent by the researchers, the audio and video files will be deleted from the secure server if in accordance with VA and MUSC policy.

Data Management Plan. Data will be coded using unique research identifications (IDs). All source documents will be labeled using the research ID and will not include identifying information. Data collected during assessment or treatment will be stored in a secure location (locked file cabinet in a locked room) and will be entered in the data management system. Raw study data will be manually entered from original and securely stored. Paper forms will be retained at the study site in secure storage per VA policy. Every member of the research team will be trained and monitored about how to handle and protect both medical and research records.

Data Sharing. Only data without identifiers will be shared between sites and all data will be retained on the VA network and REDCap.

Data and Safety Monitoring Board. The DSMB will be made up of three members: Primary Care provider, biostatistician, and a PTSD treatment researcher. They will meet a minimum of twice per year during the period of study recruitment to review data for quality, assess patient progress through the study, and examine adverse event data.

Data Analytic Plan. Baseline variables will be examined to compare PE-PC and PCMH-TAU groups using t- tests and chi-square as appropriate. Baseline variables found to be potential confounders in the relationship between treatment and outcomes will be included as covariates in outcome analyses. Although patients will be randomized to intervention groups, other potential covariates are trauma era (Vietnam, Operation Enduring Freedom (OEF)/Operation Iraqi Freedom (OIF)/Operation New Dawn (OND), Persian Gulf), baseline function level, PTSD or depression severity, and demographic characteristics.

Hypothesis 1.1: PE-PC will result in larger increases in function than PCMH-TAU (Week 0 to Week 6) and these differences will be maintained at 12 and 24 weeks post-baseline. Effectiveness will be defined as a group difference at 6 weeks, and maintenance will be defined as whether there is still a group difference at 12 and 24 weeks and whether gains relative to baseline have not been lost. To examine the effectiveness and maintenance of a brief PE-PC protocol compared to PCMH-TAU alone, we will use a unified linear mixed-effects model with WHODAS total scores at 0, 6, 12 and 24 week as the dependent variable. Mixed-effects analyses do not require the assumption of homogeneity of variance in the treatment groups, permits flexible specification of the covariance matrix of the repeated measures and gives unbiased estimate with incomplete data assuming missing at random. The model will include each participant as random intercepts and will adjust for other potentially confounding patient characteristics identified in baseline analysis. Primary predictors will be PE-PC group indicator and time (either as a continuous variable in weeks or as indicators each for 6, 12 and 24 weeks), and interactions of treatment group by appropriate time variable. In this model, time can be modeled in a variety of ways, and a graphical exploration of the cross- sectional means of the outcome by treatment group at each assessment time will guide the decision. For example, if time shows a non-linear effect (e.g., lack of maintenance at 24 weeks), we can model time as categorical indicators for each assessment time and will include interaction terms of PE-PC group indicator by time indicator. Based on the model coefficients and contrasts of the coefficients, outcome at 6 (for effectiveness), 12 and 24 weeks (for maintenance) can be compared separately between groups, and a significant drop in function from 6 to 12 and from 6 to 24 weeks within PE-PC group can be tested for any loss in initial gain (another type of maintenance) if 6 week gain is found to be significant. If no significant loss of initial gain is seen (e.g., no significant difference across the three interaction effects), we will test for the time-averaged PE-PC effect during 6-24 weeks by dropping the interaction terms, and including post randomization time indicator and its interaction with PE-PC group indicator where the coefficient of the interaction term will be interpreted as the time-averaged PE-PC effect during period 6 to 24. Although not our main hypothesis, within each treatment group, improvement from baseline in outcome at each follow-up will also be determined based on the model. Residuals will be examined for ceiling or floor effects, and if ceiling or floor effect is evident, we will consider reanalyzing function using the dichotomized WHODAS total score (using hierarchical logistic regression model and recognizing that our study will likely not have adequate statistical power for H1 based on the dichotomized response), and will also repeat the primary analysis using the overall impairment score of the B-IPF.

The study will have both drop-outs and lost to follow-up. We will prepare a consort flow diagram to describe disposition of Veterans at each stage of the research. We expect about 10% loss at 6 weeks. This estimate may seem low but the period of follow-up is short and patients will be followed regardless of treatment completion to fully model response. Primary analytic cohort will be intent-to-treat. Every effort, including follow-up phone calls, will be made to collect follow-up data to reduce missingness to a minimum. We will also collect the reason for missing data such as "patient refusal" or "scheduling complication" to have a better understanding of the mechanisms of missingness. We will check for pattern of missingness, compare rate of missingness at each follow-up time and dropouts between

groups, and compare reasons for dropout between groups. We will also check if dropout depends on covariates and will include those covariates in the models described above; the analysis using linear mixed-effects model will give us an unbiased estimate assuming missing at random. When data are missing for items within scales, we will use recommended imputation procedures.

Hypothesis 2.1-2: PE-PC will result in larger reductions in PTSD severity (H2.1: CAPS and PCL-5 (49, 50)) and depression severity (H2.2) than PCMHI-TAU (Week 0 to Week 6), and these differences will be maintained at 12 weeks and 24 weeks post-baseline, larger reductions in depression than PCMHI-TAU (Week 0 to Week 6) and these differences will be maintained at 12 weeks and 24 weeks post-baseline. We will use a similar analytic approach as for Aim 1 using a linear mixed-effects regression model for each outcome measure with both baseline and all follow-up assessment data as the dependent variable. The model will include PE-PC group indicator, follow-up time indicators, and interactions of treatment group by follow-up time indicators. Statistically significant interaction terms with negative parameter estimates will provide evidence for significantly greater symptom reduction at each follow-up time in those randomized to PE-PC compared with PCMHI-TAU group. Similar to the analytic approach described for Aim 1, maintenance will also be assessed as drop at 24 weeks in improvement gained at 6 weeks, and this will be assessed for both PTSD and depression symptoms using appropriate contrasts based on the coefficients from the linear mixed-effects model.

Hypothesis 2.3: PE-PC will result in a greater proportion of Veterans remitting from PTSD than PCMHI-TAU at week 6, 12, and 24. Remission will be defined as CAPS5 below 20. We will report proportions remitted in each treatment group with confidence intervals. To compare remission between two treatment groups at 6, 12 and 24 weeks, we will use a generalized linear mixed-effects regression with logit link. The dependent variable will be the repeatedly assessed remission at 6, 12 and 24 weeks, and the primary predictor will be the PE-PC group indicator and indicators for 12 week and for 24 week time, and the interactions of follow-up time indicators by treatment group can be used to test if the relative odds of remission between the two intervention groups differ across the follow-up times. The model will be adjusted for baseline function score and symptom severity as well as site.

For the exploratory aim to assess potential moderators of improvements in function and PTSD symptoms, potential moderators include combat experience severity, and exposure to life events. We will extend the primary mixed-effects model to include these measures and their interaction terms with PE-PC arm to understand and assess if the treatment effect differs by the level of these potential mediators. We will also extend the mixed-effects model by including PTCI as a time-dependent covariate to explore if increased self-efficacy, as assessed by PTCI, is associated with decreased function or symptom. Lastly, in the control (PCMHI-TAU) arm, we will include the use of specialty care during prior six weeks as a time- dependent covariate to see if it explains improvement in function or symptom in the control group. This exploration will provide us with an examination of whether contamination of participating study providers' referring control patients to specialty care might explain some of the improved function or symptom in control group, which might in turn have led to reduced effects of PE-PC.

Power Analysis. We propose to enroll 120 patients (60 per group) and considered power to detect a clinically meaningful difference in primary outcome at 6 months. The sample size is expected to have 80% power to detect a 0.54 standardized effect size with 0.05 two-sided tests for the outcome of WHODAS total score, assuming 10% lost- to-follow-up at the primary endpoint of 6 weeks post-baseline. This estimate of loss to follow-up may seem low but the period of follow-up is short and patients will be followed regardless of treatment completion to fully model response. The between-

group standardized effect size of 0.54 is approximately a medium effect size and is meaningful for both function and symptoms, and we consider this effect size minimally detectable with PE-PC based on our preliminary data. If no differential trends between arms is present over the 24 weeks follow-up time, we will be able to detect a smaller standardized effect size of 0.49 as a time-averaged between- arm difference with a 0.05 level two-sided test assuming within-person correlation of 0.6 and an overall 20% loss to follow-up by week 24 based on our preliminary data. For binary outcome of remission, we do not have preliminary data, but we note that we do not expect to have adequate power unless the between-arm difference in remission is very large; for example, the study will have 80% power to detect a difference of 69% vs. 42% with a 0.05 level two-sided test.

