We will examine the effectiveness (function and symptoms) of PE-PC in VHA primary care mental health integration (PCMHI) clinics. We will randomize Veterans presenting in VA PC with chronic PTSD symptoms [PCL-5 \geq 28] who meet minimal inclusion/exclusion criteria to receive PE-PC (four to six, 30-minute weekly sessions) or PCMHI treatment as usual (TAU). TAU will include the current standard of PTSD care in PCMHI (medication, referral to specialty mental health, etc.). The type of TAU used will reflect the current practice in PCMHI and will not be constrained in the study design. All care received will be closely monitored and recorded. All Veterans will complete baseline (week 0) and follow-up assessments at weeks 6 (post), 12, and 24. We will examine utilization at 24 weeks prior to randomization and 24 weeks after randomization. Project deliverables include effectiveness, acceptability, and utilization on PE-PC compared to PCMHI TAU. If effective, implementation strategies for PE-PC can be quickly developed and tested using the current dissemination infrastructure in place for the PE Therapy roll-out trainings in discussion with VA stakeholders.

Aim (1): Examine the effectiveness of PE-PC compared to PCMHI-TAU to improve functional outcomes [*Outcomes: functional impairment/quality of life (WHODAS)*].

Hypothesis 1: PE-PC will result in larger increases in *function* than PCMHI-TAU (Week 0 to Week 6) and these differences will be maintained at 12 and 24 weeks post-baseline.

Aim (2): Examine the effectiveness of PE-PC compared to PCMHI-TAU for treatment of PTSD [Outcomes: reductions in *PTSD severity* (Clinician Administered PTSD Scale (CAPS-5), PTSD Checklist- 5 (PCL-5) and *depression* (Patient Health Questionnaire-9 (PHQ-9))].

Hypothesis 2.1: PE-PC will result in larger reductions in *PTSD severity* (CAPS and PCL-5(15, 16)) than PCMHI-TAU (Week 0 to Week 6) and these differences will be maintained at 12 weeks and 24 weeks post-baseline.

Hypothesis 2.2: PE-PC will result in larger reductions in *depression* than PCMHI-TAU (Week 0 to Week 6) and these differences will be maintained at 12 weeks and 24 weeks post-baseline.

Hypothesis 2.3: PE-PC will result in a greater proportion of Veterans remitting from PTSD than PCMHI-TAU at week 6, 12, and 24.

Our exploratory aim is to assess potential moderators of improvements in function and PTSD symptoms, including combat experience severity and exposure to life events.

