4. INCLUSION AND EXCLUSION CRITERIA / STUDY POPULATION

Veterans presenting in PC with chronic PTSD symptoms (PCL-5S ≥ 28) of at least 3 months duration who meet minimal inclusion/exclusion criteria will be randomly assigned to PE-PC (four to six, 30-minute sessions) or PCMH-TAU over 4-6 weeks. Non-veterans will not be included in the study. All Veterans will complete a baseline assessment prior to randomization and post- treatment and follow-up assessments at Weeks 6, 12, and 24 post-baseline. Interview assessments will be completed via phone or face-to-face depending on patient preference. Self-reports will be completed via paper and pencil or online via REDCap. Potential Veteran participants will be any era Veterans with PTSD symptoms and desire treatment for this issue. Age range will include 18 to 70. Ralph H. Johnson VAMC (CHS and surrounding CBOCs) PCMH will conduct the study.

Inclusion Criteria:

1. Any era Veterans seeking care in VA PC for PTSD symptoms (PCL-5 ≥ 28).
2. Age 18-70.
3. English speaking.
4. Report significant impairment in function related to PTSD symptoms as noted on intake WHODAS.
5. Report that they want treatment for PTSD.

Exclusion Criteria:

1. Other primary clinical issue that would interfere with PTSD treatment.
2. Level of suicidal risk as determined by the Columbia Suicide Severity Rating Scale (C-SSRS) that requires intervention.
3. Severe cognitive impairment that, in the judgment of the investigator, makes it unlikely that the patient can adhere to the study regimen.
4. Psychosis or unmanaged bipolar disorder.
5. Moderate to severe substance use disorder in the past 8 weeks.
6. Patients who are currently receiving talk therapy for trauma- related symptoms.

Inclusion/Exclusion criteria will initially be determined by the PCMH provider at the first contact and will be confirmed by the Independent Evaluator (IE) at the Baseline assessment following consent.

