Medication Stabilization. Participants meeting inclusion criteria will be asked to maintain medications at current dosages when medically appropriate. Participants who have not initiated new psychotropic prescription medications in the previous 2 weeks will complete the baseline assessment battery. Potential participants who have recently begun trials of psychotropic prescription medication will be required to wait 2 weeks prior to completing the baseline assessment battery to ensure medication stabilization, at which point the assessment battery will be administered (or re-administered if applicable). This re-administered battery will be used for pre-treatment data in analyses.

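### Hypothesis 2.3 counts any CAPS5 below 20 at follow-up as remission, with no week-0 CAPS5 condition in the definition or at entry, so a patient already below 20 who stays there is reported as remitting

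*Combined protocol and SAP*

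**What the plan says.** Section 1 (Specific Aims), Hypothesis 2.3: "PE-PC will result in a greater proportion of Veterans remitting from PTSD than PCMHI-TAU at week 6, 12, and 24". The Data Analytic Plan in section 10 makes this operational in one sentence, "Remission will be defined as CAPS5 below 20". The outcome is scored at weeks 6, 12 and 24; week 0 is not part of the dependent variable. The plan adds "We will report proportions remitted in each treatment group with confidence intervals" and a logistic mixed model adjusted for baseline function, symptom severity and site. The severity measure is not named there. The general list of candidate covariates earlier in the plan reads "baseline function level, PTSD or depression severity, and demographic characteristics".

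Entry (section 4) is open to "Any era Veterans seeking care in VA PC for PTSD symptoms" with PCL-5 of at least 28. The opening text of that section adds a duration of at least 3 months, and the numbered list adds functional impairment on the WHODAS and wanting treatment. Eligibility "will be confirmed by the Independent Evaluator (IE) at the Baseline assessment following consent", but no listed criterion uses a CAPS5 score or a CAPS5 diagnosis. CAPS5 is nevertheless collected at weeks 0, 6, 12 and 24 (Table 1).

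Three further provisions bear on the remedy.
- Under Medication Stabilization, a battery repeated after a medication wait replaces the first: "This re-administered battery will be used for pre-treatment data in analyses".
- Data Collection (section 10) separately allows week-0 measures to be repeated when more than 4 weeks have passed since baseline.
- The plan says "Primary analytic cohort will be intent-to-treat", and Randomization Procedures (section 9) admits a patient to that set only after randomization and attendance at the first session.

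**The concern.** Remitting means moving from above a threshold to below it. The definition checks only the second half of that. Entry and outcome use different instruments, one a self-report checklist and the other a clinician interview, so nothing in the criteria rules out a patient who scores at least 28 on the PCL-5 and below 20 on CAPS5 at the same baseline visit.

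Hypothesis 2.3 is also out of line with the rest of the plan. Hypothesis 1 judges maintenance partly by gains from baseline, and Hypotheses 2.1 and 2.2 place the baseline score in the dependent variable. Only the remission outcome ignores week 0, although its wording implies change.

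What is at stake is the label and the absolute remission rates on a secondary endpoint. Those rates are likely to be read on their own, because the protocol already supports PE-PC with a single-arm figure from earlier work (half of recipients no longer meeting diagnostic criteria).

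**Working it through.** **The plan's own figure.** The Power Analysis gives 80% power for 69% vs 42%, two-sided 0.05, with 60 per group. With 10% loss at week 6 there are 60 × 0.90 = 54 per arm, and the pooled two-proportion formula gives 81.5%. The stated figure reproduces; there is no arithmetic error.

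**Coding check.** Take CAPS5 of 15 at week 0 and 15 at week 6, with PCL-5 at or above 28 and the other criteria met. Entry: eligible. Week-6 outcome: below 20, so remitted. Change: none. Covariate adjustment alters the model's arm contrast. It changes neither this code nor the reported proportions.

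**Inputs for the size.**
- p, the reported rate: 0.69 (PE-PC) and 0.42 (TAU). This is the plan's example of a detectable difference, used only for illustration.
- f, the share below 20 at week 0: not in the documents; assumed 5% or 10%.
- s, the share of those still below 20 at the visit: not in the documents; assumed 80-95%, equal in both arms.

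**Formulas.** Rate among patients at or above 20: r = (p − f·s)/(1 − f). Overstatement: p − r = f·(s − p)/(1 − f). Arm difference among patients at or above 20: (reported difference)/(1 − f).

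| f | s | r, PE-PC | r, TAU | Overstatement, PE-PC (points) | Overstatement, TAU (points) | Difference among ≥20 (points) |
|---|---|---|---|---|---|---|
| 5% | 80% | 68.4% | 40.0% | 0.6 | 2.0 | 28.4 |
| 5% | 95% | 67.6% | 39.2% | 1.4 | 2.8 | 28.4 |
| 10% | 80% | 67.8% | 37.8% | 1.2 | 4.2 | 30.0 |
| 10% | 95% | 66.1% | 36.1% | 2.9 | 5.9 | 30.0 |

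Example, f = 10%, s = 95%, TAU: 0.10 × (0.95 − 0.42)/0.90 = 0.059.

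**Share of reported remitters already low at week 0**, f·s/p. TAU: 10-11% at f = 5% and 19-23% at f = 10%. PE-PC: 6-7% and 12-14%.

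**Scale.** The 95% half-width is 1.96·√(p(1 − p)/54), which is 12.3 points at 69% and 13.2 at 42%. All shifts in the table are well inside it.

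**Direction.** The overstatement is positive only if s exceeds p. At f = 10% and s = 60%, PE-PC gives 0.10 × (0.60 − 0.69)/0.90 = −1.0 point (understated) and TAU gives 0.10 × (0.60 − 0.42)/0.90 = +2.0 points.

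**Power at f = 10%** (unadjusted; 54 × 0.90 = 48.6 per arm in the subset).
- If 69% vs 42% are the subset rates, subset power is 77%. The diluted all-patient rates f·s + 0.90p are 70.1% vs 45.8% (s = 80%) to 71.6% vs 47.3% (s = 95%), with power 73-74% at 54 per arm.
- If 69% vs 42% are the all-patient rates, subset power is about 85%, against 82%.

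**The case against.** The strongest reply is that this may hardly occur. Entry combines a checklist threshold, 3 months' duration, functional impairment, wanting treatment and confirmation by the evaluator, so f could be close to zero. That stands: nothing in the documents fixes f, and a reader should not infer that a large share of remitters would be spurious.

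It can also be said that the between-arm test is protected by randomization and already adjusts for symptom severity, that remission is not the primary outcome, and that the Power Analysis concedes low power for it. This too stands as far as the test goes. It does not reach the proportions, which the plan promises separately and which adjustment leaves unchanged.

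Three stronger readings are tempting and are not supported.
- A reader might infer that both arms' rates must be too high. That needs persistence above each arm's reported rate, and the s = 60% case shows PE-PC understated.
- A reader might infer that the definition could manufacture a PE-PC advantage. Under equal persistence the reported difference is (1 − f) times the difference among patients at or above 20, so an advantage is diluted and not created.
- A reader might infer that restricting the analysis costs a fixed amount of power. The sign depends on which population the assumed rates describe.

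Finally, relabelling the outcome and reporting the week-0 count would also close the gap in labelling. That is fair as a minimum, but it would leave Hypothesis 2.3, as worded, without an estimate.

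**Conclusion.** The point holds in limited form. Followed exactly, the plan would report as remitting from PTSD a patient whose CAPS5 was below 20 throughout. This follows from the text and needs no assumption.

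The size does rest on assumptions. With f of 5% or 10%, s of 80-95% equal in both arms, and 69% vs 42% as reported rates, the overstatement is at most 5.9 points in TAU and 2.9 in PE-PC, smaller than the sampling uncertainty of either rate. The defect concerns the label and the absolute rates of a secondary endpoint. No arm is favoured, and the WHODAS analysis and the CAPS5 severity analysis (Hypothesis 2.1) are untouched. It is worth correcting before analysis because the data needed are already being collected.

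**What to change.** In the Hypothesis 2.3 text:

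1. Report the remission proportions with confidence intervals, and the adjusted logistic mixed model, among patients in the plan's analysis set with week-0 CAPS5 of 20 or more.
2. Define week-0 CAPS5 as the last value before randomization, covering re-administration under both Medication Stabilization and the 4-week rule in Data Collection.
3. State the number below 20 at week 0 by arm.
4. Name week-0 CAPS5 as the symptom-severity covariate.
5. Keep the model and proportions in the full intent-to-treat set, labelled CAPS5 below 20 and not remission.

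The cost is a few sentences and no new data. There are four limits to state.
- The subset comparison is fully randomized only if the analysis set is all randomized patients; Randomization Procedures now restricts it to those who attend the first session.
- The denominator shrinks, to about 103 of 108 at f = 5% or 97 of 108 at f = 10%, on an endpoint the plan already calls underpowered. No fixed power loss should be quoted.
- Selecting on a single baseline score brings regression to the mean in both arms, so within-arm remission rates are not treatment effects.
- A change from 20 to 19 would still count as remission.
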